Thus, good evidence suggests that at least acute treatment with ARBs could ameliorate lung injury in COVID-19. We therefore propose to test losartan in a Phase I proof of concept and safety trial. The primary hypothesis to be tested is that losartan treatment is safe in the setting of acute SARS-CoV-2 infection. Secondarily, losartan can potentially reduce the length of respiratory failure due to SARS-CoV-2.

Significance

Importance of the problem: As outlined above, there is currently no data that supports specific treatment options for respiratory failure in COVID-19. There are active or soon to be active clinical trials that may show promise in this space such as blocking IL-6 with tocilizumab²⁰ or using hydroxychloroquine. None of these therapies are without side effects and alternative or additional approaches could lessen the burden of respiratory failure in this patient population.

Approach and Protocol

This is an open label, phase 1 clinical trial to evaluate the safety of losartan in respiratory failure due to COVID-19.

Clinical Trial setup:

Detailed inclusion and exclusion criteria are listed below. Briefly, 50 patients with COVID-19 and respiratory failure who meet criteria and agree to participation in the study will be placed on losartan 25 mg daily on study day 0. If parameters are met the dose of losartan will be increased to 50 mg on study day 3. Participants will continue losartan until they experience resolution of respiratory failure (normal oxygen levels on room air), are discharged from the hospital, meet stoppage criteria (detailed below) or complete 14 days of therapy.

Primary hypothesis and endpoint:

- Losartan is safe in acute respiratory failure due to SARS-CoV-2.

Secondary endpoints:

- Losartan reduces the number of days on supplemental oxygen in respiratory failure due to COVID-19
- Incidence of mechanical ventilation use
- Days on mechanical ventilation
- Incidence of non-invasive positive pressure ventilation or heated high flow nasal cannula use
- Days on non-invasive positive pressure ventilation or high flow nasal cannula
- Incidence of transfer to ICU from non-ICU hospital bed
- ICU length of stay (days)
- In-hospital mortality
- Hospital length of stay (days)
- Cumulative incidence of severe adverse events
- Cumulative incidence of adverse events
- Change from baseline in oxygenation

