Patients that request to not be treated with Losartan will be approached by the study team to request permission for their standard of care treatment and data be followed and recorded by the research team for this study. Patients that agree, will sign the consent form, but will not provide a blood sample for research. We will also collect medical information relating to safety criteria on historical controls treated at the University of Kansas Hospital in the 30 days prior to the study start date (3/25/2020) and during the study period. These controls will be retrospectively identified through query of the electronic health record. We will attempt to include controls that meet all criteria for enrollment into the study but to achieve a ratio of controls to study participants of 2:1 may need include some with exclusion criteria (excluding prior ACE inhibitor or ARB use). Controls identified retrospectively will not undergo informed consent as this represents minimal risk.

Losartan

Losartan is an FDA-approved ARB widely prescribed for treatment of hypertension, heart failure, and for renal protection in patients with diabetes. The doses proposed in this study are well tolerated by non-hypertensive patients without significant effect on blood pressure. The proposed starting dose of losartan is 25 mg orally per day with increase to 50 mg orally per day on day 3 if tolerated until they patient is discharged from the hospital, met stoppage criteria (above) or completed 14 days of therapy.

The most common side effects are fatigue and dizziness. Serious adverse events that are rare include angioedema, hypotension, renal dysfunction or failure, blood dyscrasias, hepatitis, or rhabdomyolysis. The following are meant to mitigate risk to the subjects: Dosing will be done in an inpatient setting with clinically indicated close observations of blood pressure and organ dysfunction (blood work). Subjects with hyperkalemia, renal dysfunction, or who are taking potassium supplements will not be enrolled into the study. Participants will be given written descriptions of potential side effects and potential responses to the side effects.

Sample size and Statistics

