Since there is no information on the effects of losartan in human beings suffering from COVID-19, a statistical analysis based on efficacy is not possible. From a safety perspective, we would accept considering losartan equivalent or superior to the comparison group not receiving losartan (historical or no consent) if there is a $\pm 20\%$ difference in total AE/SAEs. Historical controls will be matched with study participants based on upon age, sex and disease severity in a 2:1 ratio for safety comparison. From a safety perspective, losartan's long track record as a safe medication is reassuring. See section on DSMB for further details on safety monitoring and analysis.

Confidentiality

All information provided by the subject to the investigators, and all information that is collected about the subjects by the investigators, shall be kept confidential to the extent that is provided by law. Computer data files will be stored and backup up to secure, HIPPA compliant, password protected computers and servers. Electronic data capture into REDCap system will be used. Access to these databases will be restricted to individuals associated with the study who require access to the data to perform their duties. These individuals will be named by the principal investigator prior to initiation of the clinical trial. The subject's actual identity cannot be ascertained exclusively from these data and the subject's name shall not be used in any publications. All investigators and staff involved in the research protocol will be bound by this agreement of confidentiality.

Adverse Event and Serious Adverse Event Documentation

Definition of an Adverse Event

For the purpose of this protocol, an AE will be defined as any untoward medical occurrence in a subject during the study listed under DMSB - Anticipated Adverse Events and Grading Scale section of this protocol as well as safety monitoring data listed on table 1 as well as stoppage criteria for losartan.

The event does not necessarily have a causal relationship with the treatment. AEs will be collected for both study groups, treatment and control from the time the ICF is signed until the subject completes study participation.

Definition of a Serious Adverse Event

An SAE is any AE that meets any of the following outcomes:

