- Fatal (death, regardless of cause, that occurs during participation in the study or occurs after participation in the study and is suspected of being a delayed toxicity due to administration of the study drug)
- Life-threatening, such that the subject was at immediate risk of death from the reaction as it occurred
- Inpatient hospitalization or prolongation of hospitalization

- Persistent or significant disability/incapacity (disability is defined as a substantial disruption of a person's ability to conduct normal life functions)
- Congenital anomaly or birth defect
- Important medical event that, based upon appropriate medical judgment, may jeopardize the subject or may require medical or surgical intervention to prevent 1 of the outcomes listed above (e.g., an allergic bronchospasm requiring intensive treatment)

Data Safety and Monitoring Plan and Internal DSMB

Anticipated Adverse Events and Grading Scale

Losartan side effects: The most common side effects are fatigue and dizziness. Serious adverse events that are rare include angioedema, hypotension, renal dysfunction or failure, blood dyscrasias, hepatitis, or rhabdomyolysis (clinical assessment of muscle pain). Skin rashes, palpitations or other moderate or severe adverse events without other clear explanation warrants immediate cessation of treatment and notification of study personnel, who will take appropriate reporting actions.

Grading Scale

Grade 1:

Mild; asymptomatic or mild symptoms; clinical or diagnostic observations only; intervention not indicated.

Grade 2

Moderate; minimal, local or noninvasive intervention indicated; limiting age-appropriate instrumental ADL*Grade 3

Severe or medically significant but not immediately life-threatening; hospitalization or prolongation of hospitalization indicated; disabling; limiting self care ADL**.

Grade 4

Life-threatening consequences; urgent intervention indicated.

Grade 5

Death related to AE.

Activities of Daily Living (ADL)

* Instrumental ADL refer to preparing meals, shopping for groceries or clothes, using the telephone, managing money, etc.

** Self-care ADL refer to bathing, dressing and undressing, feeding self, using the toilet, taking medications, and not bedridden.

Table 1

Adverse event	Grade 1	Grade 2	Grade 3	Grade 4	Grade 5

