 - Any serious AE or SAE attributable to study drug will be shared with the medical monitor and safety and monitoring group within 24 hrs. The members will make the decision whether or not to stop the trial.
- All SAEs will be reported to the safety and monitoring group and the appropriate agencies including FDA and IRB as required.
- All adverse effects will be reported according to the rules to the FDA, the IRB and our internal DMSB
- Initial interim analysis on safety will be done after the first 5 patients and reviewed by the internal DSMB.
- The DSMB may stop the study due to safety or futility.
- All DSMB reports will be shared with the IRB.

Safety Reporting

Data monitoring plans will be implemented as follows: The study will be closely monitored by the PI and Co-PIs. Any relevant AE or SAE will be reported to the medical monitor and to the DSMB (separate charter).

- DSMB meeting will occur after the first 5 patients, 25 patients and at end of study, or more frequently if needed.
 - Safety monitoring will be done by the DSMB. Safety monitoring will be done as follows: The investigators will continuously monitor the study for side effects. If any AE or serious adverse events (SAEs) occur, the physicians will assess the event and report them to the appropriate authorities if needed as per Good Clinical Practice. Subjects might be withdrawn from the study if they experience intolerance to the study medication, initially based on the investigators' discretion.
 - All adverse effects will be discussed among the investigators
 - If deemed severe the data will be shared with the medical monitor and the safety and monitoring group. The group will make the decision whether or not to stop the trial based on safety data.
- All SAEs will be reported to the IRB and the appropriate agencies including FDA as required.

- All adverse effects will be reported according to the rules to the FDA (if needed), the IRB and the DSMB.

Safety Reviews

Safety review will occur at least every month and/or if a SAE occurs. The internal safety and monitoring group will meet after the first 5 patients, 25 patients and at end of study or more frequently if needed. If needed, the biostatics core will assist in data analysis for adverse events as well (fee for service basis). However, this is a small study.

Removal of Subjects from Study

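### The ±20% safety rule counts symptom AEs that are found differently in losartan participants and retrospective controls, a bias towards an apparent losartan excess, all else equal, of unknown size

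*Combined protocol and SAP*

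**What the plan says.** The design is stated under Approach and Protocol: "This is an open label, phase 1 clinical trial to evaluate the safety of losartan", with "50 patients with COVID-19 and respiratory failure who meet criteria" in the treated group. Sample size and Statistics gives the decision rule, a ±20% limit on the "difference in total AE/SAEs" against patients not receiving losartan, either historical or declining treatment. It adds: "Historical controls will be matched with study participants based on upon age, sex and disease severity in a 2:1 ratio for safety comparison".

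Definition of an Adverse Event admits anything in the anticipated-AE section, in Table 1 or among the stoppage criteria, and does not require a causal link to treatment. The anticipated-AE section states: "The most common side effects are fatigue and dizziness". It also names palpitations, and its Grade 1 includes mild symptoms that need no intervention.

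On how events are found in the treated group, the Losartan section says "Participants will be given written descriptions of potential side effects and potential responses to the side effects", and Safety Reporting says "The investigators will continuously monitor the study for side effects". On the historical controls, the Control section says "These controls will be retrospectively identified through query of the electronic health record"; these patients are not consented. The AE definition has collection start in both groups when the consent form is signed, which retrospective controls never do.

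**The concern.** Fatigue, dizziness and palpitations are known mainly because a patient mentions them. An open-label losartan participant has been told in writing what to look for and is under prospective study follow-up. A retrospective control is a chart, and a mild complaint that nobody wrote down does not exist for the analysis. Because causality is not required, fatigue or dizziness from COVID-19 itself counts whenever it is recorded. If the true symptom rates are equal, the recorded rates will still tend to be higher on losartan.

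Safety is the primary hypothesis, and the ±20% comparison is its only stated numerical criterion. Nothing in the protocol restricts that comparison to objective events or sets a common method of ascertainment. Part of any observed difference could therefore reflect how events were found and not what the drug did.

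**Working it through.** **Inputs from the protocol.** There are 50 losartan participants, and a 2:1 ratio gives 2 × 50 = 100 controls. The margin is ±20%. The protocol does not say whether it is relative or absolute, whether it counts events or patients, or whether it applies to a point estimate or an interval. It gives no AE rate, error level or power, so the 50 cannot be reproduced. Both main readings are worked below.

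**Assumed inputs, shown as ranges.** There is no drug effect. Let *o* be the proportion of patients with an objective event, *p* the proportion with a symptom (20-40%, equal in both groups and independent of *o*), and *c* the share of control symptoms that are charted (25-50%). Capture in losartan participants is complete.

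**Reading 1: patients with any AE, absolute points.**
- Losartan: 1 − (1 − o)(1 − p)
- Control: 1 − (1 − o)(1 − pc)
- Difference: (1 − o) × p × (1 − c)

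The low end uses p = 0.2 and c = 0.5. The high end uses p = 0.4 and c = 0.25. The last column is an exact binomial calculation with 50 v 100 patients.

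| o | Low end | High end | Chance of observed excess above 20 points |
|---|---|---|---|
| 30% | 0.7 × 0.2 × 0.5 = 7 points | 0.7 × 0.4 × 0.75 = 21 points | 6% to 53% |
| 60% | 0.4 × 0.2 × 0.5 = 4 points | 0.4 × 0.4 × 0.75 = 12 points | 2% to 13% |
| 80% | 0.2 × 0.2 × 0.5 = 2 points | 0.2 × 0.4 × 0.75 = 6 points | 0.1% to 0.6% |

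With equal ascertainment the chance is below 1% in all these settings.

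**Reading 2: event counts, relative.** Let *s* be the symptom share of all true AEs. The expected ratio is 1 / [1 − s(1 − c)]. It exceeds 1.20 when s(1 − c) > 1 − 1/1.20 = 1/6, about 17%.
- s = 20%, c = 0.5: 1/0.90 = 1.11
- s = 30%, c = 0.5: 1/0.85 = 1.18
- s = 30%, c = 0.25: 1/0.775 = 1.29
- s = 40%, c = 0.5: 1/0.80 = 1.25

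The result is sensitive to the number of objective events. With 0.3-0.5 symptoms per patient and c = 0.25-0.5, one objective event per patient gives an excess of 1.3/1.15 − 1 = 13% to 1.5/1.125 − 1 = 33%. Two per patient give 2.3/2.15 − 1 = 7% to 2.5/2.125 − 1 = 18%.

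Counts were also simulated (Poisson and negative binomial, mean 2 or 4 AEs per patient, rule applied to the point estimate). The chance of exceeding +20% was 1.6-18.6% with no bias, 19-35% at s = 20% and c = 0.5, and 41-45% at s = 30% and c = 0.5. Sampling noise alone can therefore fail a relative rule fairly often, and the ascertainment difference adds to it.

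**The case against.** The strongest counter-argument is that objective events may swamp the symptoms. Table 1 grades as AEs any haemoglobin, leukocyte or platelet value below the lower limit, small creatinine rises, and potassium or liver enzymes above the upper limit. In inpatients with hypoxic respiratory failure, most may have such an event, and the table above shows that the patient-level bias is then only a few points. This stands, and it is why no single magnitude can be given.

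Several stronger readings are tempting, and the documents do not support them.
- *A harmless drug will show an excess and fail the rule.* The Control section allows controls who meet exclusion criteria, and these may have more objective events. The net direction is unknown.
- *Losartan participants are fully and systematically questioned.* No symptom checklist or scheduled questioning is specified. Fuller capture is inferred from prospective open-label follow-up and the written information. If capture on losartan were 80%, the ratio at s = 40% and 40% capture in controls would be (0.6 + 0.32)/(0.6 + 0.16) = 1.21.
- *Muscle pain is a counted symptom.* It appears only as the way rhabdomyolysis is assessed.
- *Sedated time distorts the comparison.* Sedation can occur in both groups, controls are matched on disease severity, and the plan states no denominator.
- *All controls are chart-only.* Patients who decline losartan but consent to follow-up have AEs collected from consent, so the asymmetry is sharpest for the retrospective group.

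The rule that collection starts at consent in both groups does not answer the point, because retrospective controls sign no consent.

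**Conclusion.** The point holds as a conditional ascertainment bias. Symptom AEs enter the total, they are found by different means in the two groups, and nothing in the plan equalises this. Taken alone, the bias runs towards an apparent losartan excess.

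Its size is not known. It could be material if objective events are uncommon and charting of symptoms in controls is poor. It would be minor on a patient-level rule if around 80% of patients or more have an objective event. On counts, with full capture on losartan, it cannot by itself take the expected ratio past 1.20 unless missed control symptoms exceed about one sixth of all AEs. These statements rest on the assumed ranges above and on no true drug effect. A possible bias in the opposite direction does not repair this one; it makes the comparison harder to interpret.

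**What to change.** In Sample size and Statistics, state that the ±20% rule applies only to events abstracted by the same EHR method, over the same defined time window, in both groups. These events would be Table 1 laboratory grades from routine-care results, recorded hypotension and vasopressor use, angioedema, and death. ICU transfers that the protocol itself instructs should not be counted, because Table 1 directs transfer for some events on losartan. Report fatigue, dizziness, palpitations and other symptoms descriptively for losartan participants, alongside consenting prospective controls where collected, outside the rule.

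This costs a sentence or two and needs no new patients or procedures. The downside is that the drug's most common side effects leave the controlled decision rule, although retrospective controls cannot support that comparison. Abstracting charted symptoms in both groups would keep them in, but charting may itself be influenced by knowledge of treatment. Any difference in laboratory testing frequency between groups remains and should be reported as a limitation.

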Hemoglobin	Hemoglobin (Hgb) <LLN - 10.0 g/dL; <LLN - 6.2 mmol/L; <LLN - 100 g/L Follow up	Hgb <10.0 - 8.0 g/dL; <6.2 - 4.9 mmol/L; <100 - 80g/L ; follow up	Hgb <8.0 - 6.5 g/dL; <4.9 - 4.0 mmol/L; <80 - 65 g/L; transfusion indicated; stop losartan, follow up	Life-threatening consequences; urgent intervention indicated; stop losartan	Death
Leukocytes	<LLN - 3000/mm3; <LLN - 3.0 x 10e9 /L; follow closely	<3000 - 2000/mm3; <3.0 - 2.0 x 10e9 /L; stop losartan; follow up	<2000 - 1000/mm3; <2.0 - 1.0 x 10e9 /L; stop losartan; follow up and further investigation	<1000/mm3; <1.0 x 10e9 /L; stop losartan; follow up and further investigation	
Platelets	<LLN - 75,000/mm3; <LLN - 75.0 x 10e9 /L; follow closely	<75,000 - 50,000/mm3; <75.0 - 50.0 x 10e9 /L; follow closely, stop losartan	<50,000 - 25,000/mm3; <50.0 - 25.0 x 10e9 /L; follow closely, stop losartan,	<25,000/mm3; <25.0 x 10e9 /L; follow closely, stop losartan, transfer to ICU	
Angioedema	N/A	N/A	Angioedema occurs – mild: stop losartan, transfer to ICU	Angioedema occurs – severe tongue swelling: stop losartan, transfer to ICU	Death
Hypotension (for participants in ICU on sedation for mechanical ventilation ONLY)	Initiation of vasopressors	Increase in vasopressor dose to >0.1; stop losartan, follow up	Persistent hypotension without alternative cause; stop losartan, follow up	Irreversible end organ damage related to hypotension; stop losartan, follow up	Death
Hypotension (for participants NOT in ICU on sedation for mechanical ventilation)	Asymptomatic, intervention not indicated	Non-urgent medical intervention indicated; stop losartan, follow up	Urgent medical intervention or transfer to ICU indicated; stop losartan, follow up	Life-threatening and urgent intervention indicated; losartan, follow up	Death

Creatinine	>1 - 1.5 x baseline; >ULN - 1.5 x ULN; follow up	>1.5 - 3.0 x baseline; >1.5 - 3.0 x ULN; close follow up	>3.0 baseline; >3.0 - 6.0 x ULN; stop losartan, nephrology intervention	>6.0 x ULN; stop losartan, nephrology intervention	
Potassium&	>ULN to 5.5 mmol/L; monitor	>5.5 - 6.0 mmol/L; stop losartan, close follow up	>6.0 - 7.0 mmol/L; urgent intervention indicated, stop losartan, intervention	>7.0 mmol/L; life-threatening consequences; stop losartan, intervention	

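### Table 1 counts any creatinine above the patient's own baseline as a Grade 1 adverse event, and no rule handles values abnormal at entry, so laboratory noise enters the primary safety comparison at full weight

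*Combined protocol and SAP*

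**What the plan says.** - **What is an AE.** Under Definition of an Adverse Event, an AE is "any untoward medical occurrence in a subject during the study listed under" the anticipated-events section, "as well as safety monitoring data listed on table 1 as well as stoppage criteria for losartan". Causality is not needed: "The event does not necessarily have a causal relationship with the treatment". Collection runs "from the time the ICF is signed until the subject completes study participation".
- **Creatinine.** Table 1 sets Grade 1 at ">1 - 1.5 x baseline; >ULN - 1.5 x ULN; follow up". There is no minimum rise and no repeat test.
- **Other laboratory rows.** Haemoglobin, leukocytes, platelets, potassium, liver enzymes and CPK are graded against LLN, ULN or absolute values. No rule covers a value already in a graded band at entry.
- **Eligibility.** The exclusion criteria admit potassium up to 5.5 mM (the whole Grade 1 band) and liver tests up to 5 x ULN (Grades 1 and 2), and set no blood-count limits.
- **Primary criterion.** Sample size and Statistics accepts losartan as equivalent or superior on a ±20% "difference in total AE/SAEs". Grade, seriousness and relatedness do not restrict the count. The text does not say whether patients or events are counted, or whether 20% is absolute or relative.
- **Size.** The trial treats "50 patients with COVID-19 and respiratory failure who meet criteria", with controls matched 2:1.

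**The concern.** Safety is the primary hypothesis, and the comparison of total AE/SAEs is the only criterion stated for it. If a creatinine of 0.91 after 0.90 mg/dL is an AE, the total includes events that arise from measurement variation in both groups. The events of interest for losartan (hypotension, renal dysfunction, raised potassium) are then compared on top of that background. At stake is whether a finding of equivalence reflects the drug's safety or the way events are counted. A tighter margin or a confidence limit does not cure a loose event definition.

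**Working it through.** **The plan's own figure.** 50 treated patients and a ±20% margin are given without alpha, power or an expected AE rate, so 50 can be neither reproduced nor refuted. For a 20-point non-inferiority margin with 2:1 controls, plausible inputs require 21 to 99 treated patients.

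**Step 1: creatinine noise alone.** The number of draws is not stated; treatment lasts up to 14 days, so k = 1 to 14 later draws is assumed. If baseline and later values are exchangeable, baseline is the highest of k+1 values with probability 1/(k+1), so P(at least one value above baseline) = k/(k+1).

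| k | 1 | 3 | 7 | 14 |
|---|---|---|---|---|
| P | 50% | 75% | 88% | 93% |

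Simulation with an assumed within-patient CV of 5% to 8%, for k = 3 to 14:

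| Assumption | P(at least one above baseline) |
|---|---|
| Stable, reported to 0.01 mg/dL | 72% to 93% |
| Stable, reported to 0.1 mg/dL | 45% to 81% |
| Falling 10% after entry, either rounding | 5% to 58% |
| Falling 20% after entry, either rounding | 13% or less |

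The rounded figures move by several points with the assumed creatinine level.

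**Step 2: effect on any-AE incidence.** Let b be the share of patients with a noise AE, equal in both groups and independent of true events. Each group's rate becomes 1 − (1−b)(1−p), so the observed difference is (1−b) times the true one. Assume true rates of 20% (control) and 50% (losartan), with 100 and 50 patients. At b = 0, SE = √(0.5×0.5/50 + 0.2×0.8/100) = 0.081, and P(observed difference ≤ 20 points) = Φ((0.20−0.30)/0.081) = 11%.

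| b | Control | Losartan | Difference | Ratio | P(difference ≤ 20 points) |
|---|---|---|---|---|---|
| 0 | 20% | 50% | 30 points | 2.50 | 11% |
| 0.50 | 60% | 75% | 15 points | 1.25 | 74% |
| 0.75 | 80% | 87.5% | 7.5 points | 1.09 | 98% |

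**Step 3: effect on event counts.** With m noise events per patient in each group and 0.5 against 1.0 true events, the ratio is (m+1.0)/(m+0.5): 2.00 at m = 0, 1.33 at m = 1, 1.20 at m = 2. The absolute difference stays at 0.5 for every m; noise adds only variance to it.

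**The case against.** **During the study.** The definition speaks of untoward occurrences during the study, so Table 1 may be a list of which untoward events count, not a rule that every value in a band is an AE. This has force for entry abnormalities: that they would be counted is inferred from the absence of a rule. It does not help with creatinine, because a rise above baseline is new by construction and Table 1 grades it explicitly.

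**How many patients.** A reader might infer that most patients will have an AE from noise and that the comparison cannot fail for harm. Failure becomes impossible only when control incidence reaches 80% (100 − 80 = 20 points) or 83.3% (1/1.2, relative). A stable, finely reported creatinine can reach that (5/6 = 83% at 5 draws). With 0.1 mg/dL reporting it barely does, and with falling creatinine it does not. The documents give no draw frequency, reporting precision or variability, and no rate of entry abnormality.

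**Any abnormal value on any scale.** Only Table 1 tests in the listed direction count (low leukocytes, not high), and CPK appears to be done only when clinically indicated. Nor is masking universal. A true 10% against 30% is already exactly 20 points without noise. As counts with 0.83 noise events per patient it gives (0.83+0.30)/(0.83+0.10) = 1.215, outside a relative 20%.

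**Equal noise.** Treated patients are followed prospectively, while the historical controls come from record queries and sign no consent form to open the AE window. Unequal testing could inflate an apparent losartan excess. Small creatinine rises may also be partly signal, since renal dysfunction is an anticipated effect.

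**Other safeguards.** Severe AEs, renal replacement and mortality are separate secondary endpoints, and the DSMB reviews at 5 patients, 25 patients and study end. These limit the harm but leave the primary criterion unchanged.

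**Conclusion.** The point holds in a limited form. The plan states a rule that turns any creatinine above baseline into an AE, gives none for values already abnormal at entry, and passes both into the primary comparison at full weight.

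Over 3 to 14 draws, creatinine noise affects 75% to 93% of stable patients if values are exchangeable, and about 5% to 81% with coarse rounding or a 10% fall. If noise is similar in both groups, it pulls any-AE incidence and relative count differences towards equivalence. In the illustration, a 50% noise rate raises the chance of falling within 20 points from 11% to 74%. On a relative reading of the same case the ratio is still 1.25 at that noise rate, and drops inside the margin at 75% (1.09).

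The documents do not support the stronger statements that most patients will certainly have a noise AE, that harm cannot be detected, or that the bias always runs towards safety. Its size depends on unstated draw frequency, rounding and drift; its direction depends on equal ascertainment and on the unit and scale, which the plan leaves open.

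**What to change.** For counting in the primary comparison only, leaving the Table 1 clinical actions as they stand:

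1. Do not count the creatinine Grade 1 limb that starts at 1 x baseline. A creatinine AE then needs a value newly above ULN or more than 1.5 x baseline.
2. Count a Table 1 laboratory AE only if its grade is new or at least one grade worse than baseline. For treated patients, baseline is the last value before the first losartan dose, including standard-of-care losartan under inclusion criterion 5. For controls, it is the value at a defined index date, such as the day the inclusion criteria are first met.
3. Apply the same window and rule to treated patients and controls.

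Keep all grades of the clinical rows. A blanket Grade 2 cut-off would discard vasopressor initiation and asymptomatic hypotension, both Grade 1 in Table 1. Show hypotension, renal and potassium events separately, and list uncounted Grade 1 laboratory values descriptively. State whether patients or events are counted and whether 20% is absolute or relative.

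Separately, liver tests of 3 to 5 x ULN are not excluded at entry, yet Table 1 grades them 2 with an instruction to stop losartan. The sponsor must reconcile these passages.

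**Cost.** A wording change, plus an index date and pre-dose values to extract for controls and inclusion 5 patients; laboratory values are already collected. Fewer events are counted, very small creatinine rises are only described, and a patient whose baseline lies just inside a limit can still cross it by chance.
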